4.4.4 Exercise/Activity Level

Descriptive statistics or frequency tabulation will be provided for all evaluated parameters related to exercise/activity level (Table 14.1.5.3):

- Walk or bike at least 10 minutes (Yes, No)
- Days/week walking or biking ≥ 10 minutes
- Hours/day walking or biking (derived by total minutes/60)
- Any other activity/sports (Yes, No)
- Days/week for other activity/sports
- Hours/day for other activity/sports (derived by total minutes/60)

4.4.5 Tobacco Use

Descriptive statistics or frequency tabulation will be provided for the following parameters related to tobacco use (Table 14.1.5.4):

- Smoking status (Never Smoked, Current Smoker, Ex-Smoker)
- Number of years smoked
- Average cigarettes/day
- Average pipes/day

- Average cigars/day
- Average cigarettes, pipes or cigars/day (derived by adding average cigarettes/day, average cigars/day, and average pipes/day)

4.4.6 Alcohol and Illicit Substance Use

Frequency tabulation will be provided for the following parameters related to alcohol use (Table 14.1.5.5):

- Had alcohol in past 6 months (Yes, No)
- Drinks on a typical day (One or two, Three to five, Six or more)
- Frequency of 6+ drinks (Less than monthly, Monthly, Weekly, Daily or almost daily)
- Problem with alcohol when young (Yes, No, Declined to answer)
- Any DUI (Yes, No, Declined to answer)
- Used illicit substances in the past (Yes, No)

4.5 Prior and Concomitant Medications

Subject's current medications, including over-the-counter drugs, herbal supplements and/or vitamins, as well as those taken by the subject in the past 12 months (including previous treatments for AD) will be coded using the World Health Organization-Drug Dictionary and summarized separated for each of following two categories:

- 1) Prior medication: medication that ended before the first dose of study drug.
- 2) Concomitant medication: medication received at or after the first dose of study drug, medication that was received before initial dosing and continued after initial dosing of study drug, or medication with missing stop date.

A frequency tabulation of prior and concomitant medications will be shown by ATC class level 4 and preferred term (Table 14.1.6.1 and 14.1.6.2).

4.6 Extent of Exposure

The extent of exposure (days) per period is defined as date of last study drug intake – date of first study drug intake + 1 within each period. For subjects that have a “grace day” (i.e. they received 5 infusions over a period of 6 days instead of 5 infusions over 5 consecutive days), such dosing “grace day” is not considered an interruption. Extent of exposure as well as actual volume administered will be summarized descriptively per period and overall (two periods combined) (Table 14.1.7.1).

Descriptive statistics of actual infusion rate (mL/hour) will be summarized at each time point per infusion day (Table 14.1.7.2). The numbers of below, within and above the designated infusion rate reference will be tabulated at each time point per infusion day (Table 14.1.7.3). In addition, descriptive statistics or frequency tabulation will be provided for the following infusion parameters collected at each infusion day (Table 14.1.7.4):

- Required adjustment to flow rate (Yes, No)
- Entire assigned dose administered (Yes, No)

- Actual Volume Administered (mL)
- Maximum flow rate (mL/hour)
- Device used to administer infusion (Baxter Flo Gard, Other)

4.7 Treatment Completion

Treatment completion is calculated as the actual volume administered, as a percentage of the volume expected. The expected doses per treatment period will be calculated as [5 x total daily dose volume] for all subjects, regardless of study completion status. The expected doses overall will be calculated as [10 x total daily dose volume] for all subjects, regardless of study completion status. Treatment completion will be summarized descriptively and categorically (<75% and ≥75%) per period and overall (Table 14.1.8.1).

In addition, number of subjects completing 1-4, 5, 6-9, and 10 infusions will be summarized (Table 14.1.8.2).

4.8 Tolerability

Number of subjects completing 8 weeks (i.e. through Visit 10) after receiving at least 5 infusions, and number of subjects completing 24 weeks (i.e. through End of Study) after receiving at least 10 infusions will be tabulated (Table 14.1.9.1 and 14.1.9.2).

4.9 Visit Compliance

Number of subjects with a visit at each scheduled analysis timepoint will be summarized (Table 14.1.10.1).

Kaplan-Meier curves of the time to completion or discontinuation of the trial will be produced. Note at the final analysis all subjects will have the event of completion or discontinuation and no subjects will be censored. Log-rank test p value may be reported (Figure 14.1.10.2).

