- Changes in the Clinical Dementia Rating Scale – Sum of Boxes (CDR-SOB).
- Changes in the Alzheimer’s Disease Cooperative Study – Activities of Daily Living₂₃ (ADCS-ADL₂₃).
- Changes on the Alzheimer’s Disease Cooperative Study – Clinical Global Impression of Change rating (ADCS-CGIC).
- Changes on the Neuropsychiatric Inventory Questionnaire (NPI-Q).
- Changes in the Savonix Neurocognitive Assessments and Digit Span.

Secondary safety endpoints will be assessed as follows:

- Changes from baseline in clinical laboratory parameters.
- Changes from baseline in vital sign measurements.
- Changes from baseline in the Columbia-Suicide Severity Rating Scale (C-SSRS).
- Changes on MRI scans designed to assess for Amyloid Related Imaging Abnormalities (ARIA).

Secondary feasibility endpoint will be assessed by:

- Subject compliance with the study visit schedule and study visit procedures
- Subject retention
- Success of blinding

Exploratory endpoints will be assessed as follows:

- Changes in imaging endpoints such as volumetric MRI (vMRI), functional MRI (fMRI), and Arterial Spin Labeling (ASL)
- Changes in blood-based biomarkers
- Changes in CSF biomarkers (in participating subjects)

Population: Approximately 40 subjects between 60 and 90 years of age with a diagnosis of probable mild to moderate AD. Assuming a drop-out rate of 25%, enrollment at this level will yield approximately 30 evaluable subjects.

Phase: 2

[figure not shown]
Number of Sites: Up to 10 sites in the United States

Description of Study Agent: GRF6019: A ██████ human plasma protein fraction for IV infusion

Study Duration: Approximately 15 months

Participant Duration: Approximately 7 months

SCHEMATIC OF STUDY DESIGN

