4.2.2 SECONDARY ENDPOINTS

This study is neither designed nor powered to detect statistically significant differences in cognitive or motor domains between the Baseline and End of Study values. However secondary cognitive endpoints will be summarized over the study period from Baseline values using descriptive statistics:

- Changes in scores on the Mini-Mental State Examination (MMSE) ([Folstein 1975](#)) ([Appendix 1](#)).
- Changes in scores on the 11-item Alzheimer's Disease Assessment Scale-Cognitive Subscale (ADAS-Cog/11) ([Rosen 1984](#)) ([Appendix 2](#)).
- Changes in scores on the Grooved Pegboard Test ([Lafayette 2002](#)).
- Changes in scores on the Category Fluency Test (CFT) ([Acevedo 2000](#)).
- Changes in the Clinical Dementia Rating Scale – Sum of Boxes (CDR-SOB) ([Hughes 1982](#)) ([Appendix 3](#)).
- Changes in the Alzheimer's Disease Cooperative Study – Activities of Daily Living₂₃ (ADCS-ADL₂₃) ([Galasko 1997](#)) ([Appendix 4](#)).
- Changes on the Alzheimer's Disease Cooperative Study – Clinical Global Impression of Change (ADCS-CGIC) ([Ferris 1997](#)) ([Appendix 5](#)).

- Change on the Neuropsychiatric Inventory Questionnaire (NPI-Q) ([Kaufert 2000](#)) ([Appendix 6](#)).
- Change on the Savonix Neurocognitive Assessments and Digit Span ([Appendix 7](#)).

Secondary safety endpoints include:

- Changes from baseline in clinical laboratory parameters.
- Changes from baseline in vital sign measurements.
- Changes from baseline in the Columbia-Suicide Severity Rating Scale (C-SSRS) ([Posner 2011](#)) ([Appendix 8](#)).
- Changes on MRI scans designed to assess for ARIA.

Secondary feasibility endpoints include:

- Subject compliance with the study visit schedule, procedures, and infusions, and any required adaptations that are necessary for the study completion.
- Success of blinding. This will be assessed based on all occurrences (intentional or unintentional) of unblinding of blinded study subjects, their trial partners or study personnel (e.g. investigators, medical providers, cognitive testing raters, the Sponsor or their representatives).

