7.3 STUDY SCHEDULE

Visit windows (when noted) should be benchmarked relative to Visit 3 for a subject, such that subjects complete the entire study by Day 168 (±7 days). Study visit procedures are listed in the recommended order in which they should be completed.

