7.3.4 TREATMENT

There are two inpatient treatment periods scheduled during the trial, each with a total of 5 infusions. It is anticipated that sites will infuse subjects with 5 doses over 5 days. A “grace day” is allowed in the event of unanticipated safety or health concerns during each inpatient treatment period.

Visits 3-7 (Days 1-5) and 11-15 (Days 85*-89):

*Day 85 has a ± 7-day window. Visits 12-16 should follow consecutively.

- Perform the following procedures prior to administering study treatment:
 - Review AEs and concomitant medications
 - Obtain blood and urine samples for comprehensive laboratory panel; fasting samples preferred **(Visits 4, 6, 12, and 14 Only)**
 - Obtain samples for proteomics/epigenetics/biobanking; fasting samples preferred **(Visits 3 and 11 Only)**
 - Obtain i-STAT safety laboratory test samples and assess results before each infusion
 - Perform targeted physical exam (i.e. auscultation of heart and lungs and assessment of peripheral edema)
 - Measure and record the subject’s weight in kilograms
 - Perform 12-lead ECG **(Visit 11 Only)**
 - Ensure the subject has had an opportunity to eat a meal prior to cognitive and motor testing
 - Administer the Savonix Brief Battery
 - Perform ADAS-Cog/11 **(Visit 11 Only)**
 - Collect pre-infusion vital signs
- Administer study treatment and perform safety assessments per the Infusion Administration Manual
- Post-infusion: perform 12-lead ECG **(Visits 7 and 15 Only)**

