 1. C-SSRS
 2. MMSE
 3. Savonix Full Battery
 4. ADAS-Cog/11
- Complete MRI **(Visit 8 + 4 days Only)**
- In consenting, eligible subjects, perform final lumbar puncture (after final dosing) and obtain CSF samples for optional biomarker research **(Visit 16 or within 5 days following)**

Visit 9 (Day 28 ±7 days) and Visit 17 (Day 112 ±7 days)

- Review AEs and concomitant medications
- Collect the following:
 - Vital signs
 - Blood samples for interim safety labs (Note: Subjects randomized prior to August 30, 2018, will not participate in the additional interim safety labs at Visit 9 and Visit 17.)
 - Samples for proteomics/epigenetics/biobanking (fasting samples preferred)
- Ensure the subject has had an opportunity to eat a meal prior to cognitive and motor testing
- Perform cognitive and motor testing in the following order unless otherwise specified:
 1. Savonix Full Battery
 2. ADAS-Cog/11
 3. Grooved Pegboard

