 4. CFT
 5. CDR-SOB (subject and trial partner)
 6. ADCS-ADL₂₃ (trial partner)
 7. ADCS-CGIC (subject and trial partner)
 8. NPI-Q (trial partner self-administered; may be completed by the trial partner at any available time during the visit)

Visit 10 (Day 56 ±7 days) and Visit 18 (Day 140 ±7 days)

- Review AEs and concomitant medication
- Collect the following:
 - Vital signs
 - Blood and urine samples for comprehensive laboratory panel (fasting samples preferred)
 - Samples for proteomics/epigenetics/biobanking (fasting samples preferred)
- Ensure the subject has had an opportunity to eat a meal prior to cognitive and motor testing
- Perform cognitive assessments in the following order unless otherwise specified:
 1. Savonix Full Battery
 2. ADCS-ADL₂₃ (trial partner)
 3. NPI-Q (trial partner self-administered; may be completed by the trial partner at any available time during the visit)

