10.4.5 ADHERENCE AND RETENTION ANALYSES

Feasibility as measured by subject adherence with the study visit schedule, visit procedures, infusions, and subject retention. Subject adherence may vary across the different groups offering another feasibility measurement as would a comparison of the number of subjects who complete two series of 5 pulsed doses to subjects who complete only the first series. Reasons for study discontinuation will be compared across groups and across other subgroups of subjects, as appropriate.

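### SAP 4.9 reports attendance only, so it does not measure the protocol's secondary feasibility endpoint of compliance with the visit schedule and procedures

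*SAP*

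**What the plan says.** **Endpoint.** Protocol 4.2.2 lists as a secondary feasibility endpoint: "Subject compliance with the study visit schedule, procedures, and infusions, and any required adaptations that are necessary for the study completion". The Protocol Summary has a shorter form: "Subject compliance with the study visit schedule and study visit procedures". Protocol 10.4.5 describes the analysis in similar terms: "Feasibility as measured by subject adherence with the study visit schedule, visit procedures, infusions, and subject retention".

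**Timing rule.** Protocol 7.3 states: "Visit windows (when noted) should be benchmarked relative to Visit 3 for a subject". The ±7-day windows are then given visit by visit:
- Protocol 7.3.5: "Visit 9 (Day 28 ±7 days) and Visit 17 (Day 112 ±7 days" and "Visit 10 (Day 56 ±7 days) and Visit 18 (Day 140 ±7 days"
- Protocol 7.3.4, for Visit 11: "Day 85 has a ± 7-day window"
- Protocol 7.3.6: Visit 19, Day 168, with the same tolerance

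**Planned analysis.** SAP 4.9, headed Visit Compliance, has two outputs. The first is the count: "Number of subjects with a visit at each scheduled analysis timepoint will be summarized (Table 14.1.10.1", in the Safety Set. The second is a Kaplan-Meier figure of time to completion or discontinuation, which addresses retention. SAP 2.3 assigns each assessment a day relative to first dose and uses all scheduled post-dose assessments. It leaves repeat and unscheduled ones out of per-timepoint summaries. It defines no visit window.

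**The concern.** The endpoint has four parts: schedule, procedures, infusions and adaptations. Infusions are well covered in SAP 4.6 and 4.7. For the schedule, SAP 4.9 substitutes whether a visit took place for whether it took place when due. Procedures and adaptations have no dedicated summary. SAP 8, which lists changes from the protocol, does not mention this narrowing.

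The protocol (2.2) expects this trial to prepare the ground for larger ones. The design asks for inpatient stays of up to 7 nights in each dosing period, repeated cognitive batteries, informant scales and repeat MRI. Whether subjects can keep to that schedule and finish the assessments is something the next protocol needs to know. A reader of the study report will probably take a table headed Visit Compliance as the answer, although its figure drops only when a visit is missed outright.

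**Working it through.** The documents state no compliance rate, target or threshold, so there is no figure to reproduce. The check is a comparison of text, followed by an illustration on stated assumptions.

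**1. Endpoint against planned outputs**

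| Part of the endpoint | Output in the SAP | What it gives |
|---|---|---|
| Visit schedule | Table 14.1.10.1 (SAP 4.9) | Subjects with a visit at each timepoint; no window applied |
| Procedures | No dedicated table | n per timepoint in the efficacy and safety tables; MRI only listed (SAP 6.7) |
| Infusions | Tables 14.1.7.1 to 14.1.8.2 (SAP 4.6, 4.7) | Exposure, volume given, infusions completed |
| Required adaptations | No dedicated table | Infusion flow-rate adjustments only (SAP 4.6) |

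**2. Visits affected**

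Target day ±7 gives these windows:
- Visit 9: Days 21 to 35
- Visit 10: Days 49 to 63
- Visit 11: Days 78 to 92
- Visit 17: Days 105 to 119
- Visit 18: Days 133 to 147
- Visit 19: Days 161 to 175

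With 40 randomized subjects this is at most 6 × 40 = 240 visits. With the protocol's 25% drop-out, 40 × 0.75 = 30 evaluable subjects. If only those 30 go on and all attend, it is 6 × 30 = 180 visits.

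Example: a scheduled Visit 17 held on Day 125 is 125 − 119 = 6 days past its window and 133 − 125 = 8 days before the Visit 18 window opens. Nothing in SAP 2.3 or 4.9 separates it from a Visit 17 held on Day 112.

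**3. Possible gap at one timepoint (illustration)**

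Let a be the proportion attending, and q the assumed share of attended visits that are off-window or incomplete. Compliance is a × (1 − q) and the gap is a × q. Take a = 36/40 = 90%, with all 40 regarded as due:

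| Assumed q | Attendance shown | In window and complete | Gap (points) |
|---|---|---|---|
| 0% | 90% | 90% | 0 |
| 5% | 90% | 85.5% | 4.5 |
| 10% | 90% | 81% | 9 |
| 20% | 90% | 72% | 18 |
| 30% | 90% | 63% | 27 |

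At q = 30% the gap is 22.5 points with 30/40 attending and 30 points with 40/40.

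**4. Subjects with at least one off-window visit (illustration)**

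For a subject attending all six windowed visits, each with independent chance p of being off-window, the probability of at least one is 1 − (1 − p)^6:
- p = 5%: 1 − 0.95^6 = 26.5%
- p = 10%: 1 − 0.90^6 = 46.9%
- p = 20%: 1 − 0.80^6 = 73.8%

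The SAP 4.9 count would reflect none of these. Both 36/40 and every value of q and p are assumptions.

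**The case against.** The SAP is not blind to timing or completion outside section 4.9.

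- **Deviations.** Protocol 13.3 makes any noncompliance a deviation and classes persistently missed or incomplete procedures as Major. SAP 2.4 uses out-of-window as a deviation type. Table 14.1.3.1 tabulates subjects by coded deviation and severity.
- **Listings.** Listings 16.2.1.4 (deviations) and 16.2.1.6 (study visits) will hold the detail, and SAP 2.3 gives every assessment a relative day.
- **Per-visit n.** Under SAP 2.6 the change-from-baseline tables show the number of observations at each planned timepoint, so an attended visit without an ADAS-Cog lowers n.
- **Unseen layout.** The mock shells are a separate document, so the final form of Table 14.1.10.1 cannot be judged fully from one sentence.
- **Rank.** The primary feasibility endpoint is the number of subjects completing 5 and 10 infusions (protocol 4.2.1), which SAP 4.7 analyses.

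Most of this stands, and it limits the point without removing it. Table 14.1.3.1 counts subjects with a deviation, with no denominator of visits or procedures due. Its codes sit in a Protocol Deviation Plan that is not part of these documents, so it is unclear how finely it would separate one late visit from several. The out-of-window entry in SAP 2.4 serves only to define the per-protocol set, and only for efficacy procedures with a consistent pattern or a risk to the data. Listings are not summaries. The efficacy n is confined to the Evaluable and Per Protocol sets, and Savonix data are outside the eCRF database (SAP 1.5).

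A reader might infer that compliance will be overstated. The documents do not show that: they give no rate of off-window visits, and for procedures there is no dedicated completion figure to overstate, so that part is an omission. Nor do they support the inference that visit timing is lost altogether.

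**Conclusion.** SAP 4.9 measures attendance and does not deliver the schedule and procedure parts of the declared secondary feasibility endpoint; the narrowing is not recorded in SAP 8. The count can overstate schedule compliance if attended visits fall outside the ±7-day windows. The size is unknown: zero if every visit is on time and complete, and 27 points at a timepoint with 90% attendance if 30% of attended visits were off-window or incomplete. That range depends wholly on the assumed share.

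The importance is moderate. This is part of a descriptive secondary endpoint with no target or required test. A reader might infer, because feasibility belongs to the primary objective, that a primary endpoint goes unanalysed. It does not, since completed infusions have their own table. The change is still worth making, because a declared endpoint is only partly analysed and the data are largely already collected.

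**What to change.** Extend Table 14.1.10.1, by dose group and visit in the Safety Set, with subjects due as the denominator:

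1. n (%) attended, labelled as attendance.
2. n (%) attended within the protocol 7.3 window, counted from Visit 3.
3. n (%) with each procedure due at that visit completed. After screening, MRI counts only at Visits 8 (with its +4-day allowance) and 19. CSF counts only in consenting subjects. Interim safety labs at Visits 9 and 17 are not due for subjects randomized before 30 August 2018.
4. A summary of required adaptations.

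Name rows 2 and 3 as the compliance endpoint. Define in the SAP when a subject counts as due, so that drop-out, which the retention outputs cover, is not mixed with missed visits.

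Use eCRF dates where they exist, central-lab transfers for laboratory panels, and the Savonix completion statistics (protocol Appendix 7) for that battery. Confirm the source for imaging and CSF completion, since SAP 1.5 places imaging and biomarker data outside the eCRF database.

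If the team prefers to rely on Table 14.1.3.1, SAP 8 should say so. That would declare the narrowing but would not measure the endpoint.

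Cost: one extended descriptive table, some extra data handling for sources outside the eCRF, and a reported compliance figure that may be less favourable.

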7.3.6 FINAL STUDY VISIT

Visit 19, End of Study (Day 168 ±7 days)

- Review AEs and concomitant medication
- Collect the following:
 - Vital signs and subject's weight in kilograms
 - Blood and urine samples for exit laboratory panel (fasting samples preferred)
 - Samples for proteomics/epigenetics/biobanking (fasting samples preferred)
- Perform the physical exam
- Ensure the subject has had an opportunity to eat a meal prior to cognitive and motor testing
- Perform cognitive and motor testing in the following order unless otherwise specified:

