2.2 Statistical Hypothesis Tests

Inasmuch as the study design is focused on safety and tolerability, the statistical approach taken with the secondary endpoints will be primarily descriptive with only modest amounts of hypothesis testing; within-subject changes from baseline for each dosing group and between-group differences will be evaluated for the purpose of designing future studies. Inferential statistics for any within-group and between-group comparisons will be described for each specific endpoint as applicable. For all statistical tests, the nominal two-sided p values will be reported.

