4.1 Disposition Information

Summaries will be provided for the following disposition information: Number of subjects screened, screening failures, randomized, completed study, discontinued study with the reasons of discontinuation from study, discontinued from study drug with the reasons of discontinuation from study drug, and discontinued from study but completed study drug dosing. The randomized treatment group will be shown for ITT set (Table 14.1.2).

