Table 14.1.4.2	Baseline Assessment of Columbia-Suicide Severity Rating Scale (C-SSRS)	SAF
Table 14.1.4.3	APOE Genotype	SAF
Table 14.1.5.1	Medical History	SAF
Table 14.1.5.2	Social History	SAF
Table 14.1.5.4	Exercise-Activity Level	SAF
Table 14.1.5.5	Tobacco Use	SAF
Table 14.1.5.6	Alcohol and Illicit Substance Use	SAF
Table 14.1.6.1	Prior Medication	SAF
Table 14.1.6.2	Concomitant Medication	SAF
Table 14.1.7.1	Exposure to Study Drug	SAF
Table 14.1.7.2	Actual infusion rate at each time point per infusion day	SAF
Table 14.1.7.3	Numbers of below, within and above the designated infusion rate reference	SAF
Table 14.1.7.4	Overall infusion parameters per infusion day	SAF
Table 14.1.8.1	Completion of Study Drug	SAF
Table 14.1.8.2	Number of subjects completing 5 and 10 infusions	SAF
Table 14.1.9.1	Number of subjects completing 8 weeks after receiving at least 5 infusions	SAF
Table 14.1.9.2	Number of subjects completing 24 weeks after receiving at least 10 infusions	SAF
Table 14.1.10.1	Visit Compliance	SAF
Figure 14.1.10.2	Kaplan-Meier curves of the time to completion or discontinuation of the trial	SAF
Table 14.2.1	Changes in scores on the Mini-Mental State Examination (MMSE)	EVAL, PPROT
Table 14.2.2	Changes in scores on the 11-item Alzheimer's Disease Assessment Scale-Cognitive Subscale (ADAS-Cog/11)	EVAL, PPROT
Table 14.2.3	Changes in scores on the Grooved Pegboard Test	EVAL, PPROT
Table 14.2.4	Changes in scores on the Category Fluency Test	EVAL,

Number	Title	Population
	(CFT)	PPROT
Table 14.2.5	Changes in the Clinical Dementia Rating Scale – Sum of Boxes (CDR-SOB)	EVAL, PPROT
Table 14.2.6.1	Changes in the Alzheimer’s Disease Cooperative Study – Activities of Daily Living23 (ADCS-ADL23) for Subjects	EVAL, PPROT
Table 14.2.6.2	Changes in the Alzheimer’s Disease Cooperative Study – Activities of Daily Living23 (ADCS-ADL23) for Partners	EVAL, PPROT
Table 14.2.7	Changes on the Alzheimer’s Disease Cooperative Study – Clinical Global Impression of Change (ADCS-CGIC)	EVAL, PPROT
Table 14.2.8	Change on the Neuropsychiatric Inventory Questionnaire (NPI-Q)	EVAL, PPROT
Table 14.3.1.1.1	Overall Summary of Treatment-Emergent Adverse Events (TEAE)	SAF
Table 14.3.1.1.2	Overall Summary of Treatment-Emergent Adverse Events (TEAE) in Period 1	SAF
Table 14.3.1.1.3	Overall Summary of Treatment-Emergent Adverse Events (TEAE) in Period 2	SAF
Table 14.3.1.2.1.1	Incidence of Treatment-Emergent Adverse Events (TEAEs) by MedDRA System Organ Class and Preferred Term	SAF

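### SAP 4.9 treats study completion and discontinuation as one Kaplan-Meier event with no censoring, so the retention curve ends at zero in both arms and the log-rank test mixes dropout with final-visit timing

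*SAP*

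**What the plan says.** SAP 4.9 (Visit Compliance) says that Kaplan-Meier curves of the time to completion or discontinuation will be produced, and adds: "Note at the final analysis all subjects will have the event of completion or discontinuation and no subjects will be censored". A log-rank p value may be reported with the figure. The list of outputs in SAP Section 10 gives Figure 14.1.10.2 the matching title, "Kaplan-Meier curves of the time to completion or discontinuation of the trial". Under SAP 2.2, "For all statistical tests, the nominal two-sided p values will be reported".

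Protocol 7.3.6 places the final visit, Visit 19, at Day 168 ±7, that is Days 161 to 175. The Protocol Summary lists "Subject retention" as a secondary feasibility endpoint. Protocol 10.4.5 describes "Feasibility as measured by subject adherence with the study visit schedule, visit procedures, infusions, and subject retention". Neither document defines a time-to-discontinuation analysis in which completers are censored. SAP 4.1 does count subjects under "completed study, discontinued study with the reasons of discontinuation from study".

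**The concern.** Completing the trial is the good outcome for retention and discontinuing is the bad one. Merging them has two consequences.

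- **The curve.** It cannot level off at the proportion retained. It reaches zero at each arm's last exit, so its end point says nothing about dropout.
- **The test.** A fully retained subject seen on Day 161 counts as an earlier failure than one seen on Day 175. With most subjects completing, most of the events are scheduled final visits.

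Figure 14.1.10.2 is the only time-to-event display of retention in the SAP, and its log-rank test is the only between-group test named for it. A non-significant p value could be read as similar retention in the two dose groups when the test was insensitive to dropout. If final visits happened to fall earlier in one arm, a small p value could appear with equal dropout.

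**Working it through.** **Inputs from the documents.** There are 20 subjects per arm (SAP 1.2). Assumed dropout is 25%, leaving about 30 of 40 evaluable (Protocol Summary). Visit 19 falls on Days 161 to 175. SAP 4.9 gives the event definition and the no-censoring rule. No significance level is stated for the log-rank test, so two-sided 0.05 is assumed.

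**The plan's own figure.** 40 × (1 − 0.25) = 30, as the Protocol Summary says. The documents give no power or event count for this analysis. If the same 25% is used as the dropout rate, about 30 of the 40 events (75%) would be completions and about 10 would be dropouts.

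**Curve.** Take an arm of 20 with dropouts on Days 20, 50, 80, 110 and 140, and five completers on each of Days 165, 168 and 171.

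| Day | SAP 4.9 coding | Completers censored |
|---|---|---|
| 140 | 0.75 | 0.75 |
| 165 | 0.50 | 0.75 |
| 168 | 0.25 | 0.75 |
| 171 | 0.00 | 0.75 |

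The two agree until the first completion. After that only the censored version shows the proportion retained.

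**Log-rank mechanism.** At each event time, with d events among n at risk and n₁ of those at risk in the index arm:

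- expected events: E = d·n₁/n
- variance: V = d·(n₁/n)(1 − n₁/n)(n − d)/(n − 1)
- statistic, after summing over event times: (O − E)²/V on 1 df

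Illustrative data: 2 dropouts in one arm (Days 50, 110) and 8 in the other (Days 20, 35, 50, 65, 80, 110, 125, 140). Completers in both arms are split equally over Days 165, 168 and 171. The index arm is the one with 8 dropouts.

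| Coding | O | E | O − E | V | χ² | p |
|---|---|---|---|---|---|---|
| SAP 4.9 | 20 | 16.60 | 3.40 | 5.37 | 2.15 | 0.143 |
| Completers censored | 8 | 4.60 | 3.40 | 2.45 | 4.71 | 0.030 |

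The signal, O − E, is identical. The completions on Days 165 and 168 add 1.66 + 1.26 = 2.92 to the variance and nothing to the signal; those on Day 171 add zero. The power loss is this dilution.

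**Simulation.** 20 per arm and 4,000 runs per scenario, so the Monte Carlo standard error is at most √(0.25/4000) = 0.8 points. Assumptions not taken from the documents: the dropout rates, dropout uniform over Days 1 to 160, and completion on whole days about Day 168 with SD 3, kept within Days 161 to 175.

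| Dropout in the two arms | SAP 4.9 coding | Completers censored |
|---|---|---|
| 25% / 25% | 5.2% | 4.8% |
| 15% / 15% | 5.8% | 4.7% |
| 15% / 35% | 14% | 31% |
| 10% / 40% | 25% | 62% |
| 5% / 45% | 42% | 89% |

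The first two rows are false-positive rates and the rest are power. The power retained is 14/31 = 45%, 25/62 = 40% and 42/89 = 47%, so more than half is lost each time. With SD 2, or completion uniform over the window, the 10%/40% case gives 24–26% against 61–62%.

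**If final-visit timing differs between arms**, with equal dropout of 10–25%, false positives under the SAP coding are about 11–13% for a 1-day mean difference. For a 2-day difference they are about 25–39%; separate runs put the 10% dropout case between 37% and 42%. With completers censored they stay at about 4–5%.

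**The case against.** The strongest reply is that the power loss depends on the time scale, which SAP 4.9 does not state. If every completer is placed at Day 168, everyone still at risk has the event together. Then n = d, so V = 0 and O − E = 0 at that time, and the two codings give the same test. With exits grouped in weeks, the 10%/40% case is roughly 37–42% against 60–63%, a loss of about a third. This stands as a condition on the size of the effect. However, SAP 2.3 counts assessment days from actual visit dates, so actual days is the likelier reading, and the curve still ends at zero on any scale.

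The false-positive case is hypothetical. Both arms share one visit window in a randomised, double-blind trial, and the documents predict no timing difference. This also stands, so those figures should not drive the rating. The power loss needs no such difference.

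It is also fair to say that little about retention is lost overall. The curve can be read just before Day 161. Table 14.1.2 separates completers from discontinuations, SAP 4.8 tabulates completion at 8 and 24 weeks, and Table 14.1.10.1 shows attendance by visit. The p value is optional and nominal, and Protocol 4.2.2 does not repeat retention in its feasibility list. These points limit the importance but do not repair the figure or the test. The figure itself is planned without condition; only the p value is optional.

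**Conclusion.** The concern holds. As written, both curves must reach zero at end of study regardless of retention, and the log-rank test counts final visits as failures. Those two consequences follow from the definition and rest on no assumption.

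The size of the power loss does rest on assumptions: 20 per arm, exits timed in actual days, and the dropout and visit patterns given above. Under these, more than half the power for a dropout difference is lost, while the false-positive rate stays near 5% if timing is the same in both arms. Even the corrected test has only about 31% power for 15% versus 35% dropout, so at this sample size neither version reliably detects a moderate difference.

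No primary endpoint is affected. This should be fixed because the definition is wrong for retention and the correction is cheap, not because a main conclusion depends on it.

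**What to change.** Replace the text in SAP 4.9 with: *Kaplan-Meier curves of time to study discontinuation will be produced. The event is discontinuation from the study for any reason; subjects who complete the study are censored at their End of Study (Visit 19) date.* Base any log-rank p value on this definition, and retitle Figure 14.1.10.2 *Kaplan-Meier curves of time to study discontinuation*.

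In the same edit, state the time origin and unit, and which date counts as discontinuation. Protocol 5.4.2 encourages withdrawn subjects to complete end-of-study procedures within 4–6 weeks of their last visit, so candidate dates could differ by weeks. The current SAP text leaves this open as well.

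The main change costs two sentences, one figure title and one censoring flag in the program, plus a short clause for the dates. No new data are needed, since completion and discontinuation status already feed Table 14.1.2.
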